  - 1.3.1. Secondary Objective 1: To compare the total number of days of postpartum bleeding in the immediate versus standard group at 2, 4, and 8 weeks postpartum . Our hypothesis is that number of days of bleeding in the immediate insertion group is not significantly different than the number of days of bleeding in the standard insertion group.
  - 1.3.2. Secondary Objective 2: To compare postpartum sexual function as measured by Female Sexual Function Index (FSFI) score at 4, 8, and 12 weeks postpartum. Our hypothesis is that FSFI scores for the immediate insertion group are not significantly different than FSFI scores for the standard insertion group.

PROTOCOL TITLE: Effect of immediate versus standard postpartum insertion of the contraceptive implant on breastfeeding outcomes

- 1.3.3. Secondary Objective 3: To compare postpartum mood as measured by EPDS score at 2, 4, and 8 weeks postpartum. Our hypothesis is that EPDS scores for the immediate insertion group are not significantly different than EPDS scores for the standard insertion group.
- 1.3.4. Secondary Objectives 4: To compare exclusive breastfeeding through 6 months postpartum between the immediate versus the standard group.
- 1.3.5. Secondary Objective 5: To compare postpartum factors associated with discontinuing breastfeeding between the immediate versus the standard group.
- 1.3.6. Secondary Objective 6: To compare timing of breastfeeding discontinuation through 6 months postpartum between the immediate versus the standard group.
- 1.3.7. Secondary Objective 7: To compare participant satisfaction with postpartum contraception counseling in women enrolled in the study and in those women who opted not to enroll in the study.
- 1.3.8. Secondary Objective 8: To compare participant satisfaction with timing of ENG implant insertion between the immediate versus the standard group.

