**Regarding secondary objectives:**

1. Bleeding patterns: Irregular bleeding is the most common side effect noted by users of the ENG contraceptive implant. Limited evidence shows that this holds true in the postpartum period (17). In a retrospective cohort study of women who underwent immediate versus standard postpartum insertion of the implant, approximately one in five women requested discontinuation of use due to irregular bleeding, and this rate was not significantly different between the two groups (17). Evidence on the effect of immediate postpartum insertion of the ENG contraceptive implant on lochia is limited and mixed. An RCT of immediate versus standard postpartum insertion of the six-rod levonorgestrel implant showed significantly more total days of bleeding for the immediate insertion group (18), while a more recent Australian prospective cohort study demonstrated no lengthening of the duration of lochia (postpartum bleeding) with immediate insertion (19). We will measure postpartum bleeding patterns using periodic review of a patient bleeding diary that quantifies bleeding on a daily basis as “none”, “spotting”, “bleeding” or “heavy bleeding”. As patient dissatisfaction with irregular bleeding likely mediates discontinuation for this reason, we will also measure patient satisfaction with their bleeding pattern postpartum.

PROTOCOL TITLE: Effect of immediate versus standard postpartum insertion of the contraceptive implant on breastfeeding outcomes

2. Postpartum mood changes: It is possible that postpartum use of an ENG implant may affect postpartum mood. In a retrospective study of adverse event reporting for ENG implant use, it was noted that postpartum depression was a commonly reported adverse event, and therefore may be associated with implant use in the postpartum period (20). In addition, in a secondary analysis study, use of the ENG implant in the postpartum period was associated with a higher risk of later antidepressant use compared to women with no hormonal contraceptive use (21). Women's perception of contraceptives' effect on their mood is a significant factor in contraception discontinuation (22). We hypothesize that timing of implant insertion will not increase postpartum depression related mood changes as measured by the EPDS. We will also assess patient perception of impact of ENG implant insertion on mood.

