EPDS results will be scored weekly as they are obtained. The research coordinator will forward scores to the on-call study co-investigator as soon as possible/on the day they are obtained. For scores <10 (with a score of 0 for question 10) no immediate action is needed, and the study participant will be reevaluated at the next study interval. For scores < or = to 10 (with a score of 0 for question 10), the co-investigator will 1) call the study participant as soon as possible/on the day they are obtained and offer referral to counseling and/or for suicidal ideation, to the crisis hotline number (National Suicide Prevention [contact]). For women without suicidal ideation or acute crisis, the study co-investigator will offer an appointment in the OB-GYN perinatal mood disorders clinic, Journeys with a counselor within the next 5 days. Study participants with a non-zero score for question 10 will be contacted by the study co-investigator as soon as possible/on the day they are obtained by telephone and suicide risk will be assessed using the SAHMSA SAFE-T 5-step method (23). For moderate and high-risk study participants, immediate referral to UNM Psychiatric Urgent Care Clinic or Psychiatric Emergency Services will be made in addition to provision of the crisis hotline number above. All study co-investigators are competent to manage patient responses on the Edinburgh.

- 18.2. NA, no procedures may have risks to the subjects that are currently unforeseeable.
- 18.3. NA, no procedures may have risks to an embryo or fetus should the subject be or become pregnant. The implant is a contraceptive method.
- 18.4. NA, there is no risks to others who are not subjects.
- 18.5. To minimize the probability or magnitude of risks of this study the insertion will be performed as per FDA guidelines. However, side effects cannot be prevented.

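### The EPDS follow-up rule in section 18.1 has one sign reversed: low totals get two opposite instructions and totals of 11 or more get none

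*Combined protocol and SAP*

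**What the plan says.** Section 18.1 (Risks to Subjects), in the part on postpartum mood data, sets out what staff do with an EPDS result.

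- **Routing.** "The research coordinator will forward scores to the on-call study co-investigator as soon as possible/on the day they are obtained".
- **First branch, question 10 scored 0.** "For scores <10 (with a score of 0 for question 10) no immediate action is needed, and the study participant will be reevaluated". The repeat assessment comes with her following scheduled contact.
- **Second branch, question 10 also scored 0.** "For scores < or = to 10 (with a score of 0 for question 10), the co-investigator will 1) call the study participant" and offer referral to counseling or, for suicidal ideation, a crisis line.
- **Follow-on step.** "For women without suicidal ideation or acute crisis, the study co-investigator will offer an appointment in the OB-GYN perinatal mood disorders clinic", with a counselor, within five days. This sentence has no score limit of its own.
- **Third branch, triggered by question 10 and not by the total.** "Study participants with a non-zero score for question 10 will be contacted by the study co-investigator" by telephone, with a structured suicide-risk assessment.
- **Staff.** "All study co-investigators are competent to manage patient responses on the Edinburgh".

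The EPDS is also a secondary outcome. Section 1.3.3 states the aim: "To compare postpartum mood as measured by EPDS score at 2, 4, and 8 weeks postpartum".

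**The concern.** Both score-based branches carry the same condition on question 10, so only the total can separate them, and as written it does not. The first branch takes totals below 10. The second takes totals of 10 or below, which contains the whole of the first. One says to wait for the next interval and the other says to call. Above 10, neither applies.

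The group left without a stated response is the one for which such a rule exists: women with a raised total who do not report self-harm thoughts on question 10. The call branch offers counseling, a crisis line and a mood-disorders appointment. Those responses suit high totals, yet the text attaches them to low ones.

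The plan treats mood as a possible harm of the implant. Section 18.1 lists mood swings and depressive mood among its side effects. Section 2.3 cites adverse event reports of postpartum depression, while stating the study's own expectation: "We hypothesize that timing of implant insertion will not increase postpartum depression related mood changes as measured by the EPDS". Women may complete the questionnaires remotely through a link (section 12), minors from age 13 may be enrolled at one site (section 4.2), and two sites work from this protocol. With no clinician necessarily present when the form is completed, the written rule has to be right.

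**Working it through.** No sample size, power or error-rate figure bears on this point. The check is to apply each branch to every possible total and count how many instructions result.

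**Inputs, all from section 18.1, for question 10 = 0 and integer total s:**

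- Branch 1 (no immediate action, re-evaluate): s < 10.
- Branch 2 (call and offer referral), as written: s ≤ 10.
- Branch 3 (suicide-risk assessment): requires question 10 > 0, so it cannot apply here.

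The documents do not state the maximum EPDS score, and the result does not need it.

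**As written:**

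| Total s | s < 10 | s ≤ 10 | Instruction |
|---|---|---|---|
| 0 to 9 (10 totals) | true | true | wait, and also call |
| 10 (1 total) | false | true | call only |
| 11 or more | false | false | none |

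**With branch 2 changed to s ≥ 10:**

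| Total s | s < 10 | s ≥ 10 | Instruction |
|---|---|---|---|
| 0 to 9 | true | false | re-evaluate only |
| 10 or more | false | true | call and referral only |

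Overlap falls from 10 totals to 0, and the gap from 11 upward closes. A non-zero question 10 goes to the third branch before and after the change, whatever the total.

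**Does another section supply a cut-off?** The EPDS also appears in section 1 (objectives 1.1, 1.3 and 1.3.3), section 2.3 (mood), section 7 (schedule and endpoints) and section 12 (instrument table). Each gives its purpose or timing, and none gives an action threshold. The monitoring plan in section 14 gives none either.

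**Does the follow-on sentence close the gap?** The five-day appointment has no score limit, so in isolation it could reach a woman scoring 11 or more. In sequence, however, it describes what the co-investigator offers during the call, and the call is triggered only by the second branch.

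**The case against.** The strongest reply is that no trained reader would follow the sign as printed. The order of the sentences makes the intention plain. Scores go to an on-call co-investigator, and the plan states that these clinicians can manage EPDS responses. Any non-zero answer to question 10 is dealt with separately. Section 9.3 says psychological resources are available in both health systems, and section 14 has an independent physician review symptoms at least quarterly. On this view it is a one-character slip outside the analysis and deserves a lower grade.

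Most of that is true, and it limits the likely harm. It does not make the rule right. Competent staff are still given contradictory instructions for 0 to 9 and none for 11 or more. Quarterly review and general resources supply neither a threshold nor a prompt response.

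Three smaller points deserve a fair hearing:

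- **PDF reading.** A misread symbol cannot be wholly excluded. It is unlikely, because the comparison is partly spelled out in words and the signs around 37 weeks in section 4.2 came through intact. A look at the source file settles it.
- **The lone '1)'.** The second branch has a '1)' and no '2)'. This is weak evidence of lost text, since list numbering slips elsewhere too (sections 4.1, 8.2, 12.2 and 20.1). It justifies checking the sentence and adds nothing to the seriousness.
- **Timing.** The section refers to weekly scoring, and asks for forwarding and calls as soon as possible or on the day scores are obtained. The text therefore does not strictly guarantee a same-day response, and the protection from prompt routing should not be overstated.

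**Conclusion.** The concern holds. With question 10 scored 0, ten totals (0 to 9) carry opposite instructions, one total (10) carries only the call, and totals of 11 or more are named by no score-based branch. This is the only EPDS action threshold in the documents.

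That 'greater than or equal to 10' was meant is an inference, but a strong one: it is the complement of the first branch, it fits the response offered, and it leaves each total with a single instruction. The finding assumes that the symbol was read correctly from the source.

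It should be corrected because it is a wrong decision threshold in a participant-safety rule and costs almost nothing to put right. The documents support no estimate of delay or of the number of women affected, and none is made. Sample size, power, type I error and the analysis of EPDS as an outcome are unaffected.

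**What to change.** In the second EPDS branch of section 18.1, replace 'less than or equal to 10' with 'greater than or equal to 10'. The rule then reads:

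- Question 10 = 0 and total 0 to 9: re-evaluate at the next study interval.
- Question 10 = 0 and total 10 or more: call as soon as possible or on the day the score is obtained, and offer referral.
- Question 10 above 0, at any total: the existing suicide-risk assessment, unchanged.

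The responsible clinicians should confirm the whole sentence, including whether an item '2)' was dropped. At the same time they can make clear how weekly scoring fits with action on the day.

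The cost is one sign and a clinician's check of that sentence. No new data, visits or analyses are needed.

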## **19. Potential Benefits to Subjects**

- 19.1. The completion of this study will show whether women randomized to immediate implant insertion is non-inferior in terms of breastfeeding continuation through 8 weeks postpartum when compared to women randomized standard insertion. The contribution of the proposed research is to determine if inserting the implant in the first 24 hours postpartum interfere with continuation of lactation. This contribution to the literature is significant because current recommendation and previous studies are limited and insufficient.

**PROTOCOL TITLE:** Effect of immediate versus standard postpartum insertion of the contraceptive implant on breastfeeding outcomes

19.2 There may not be direct benefit to the study participants. However, their participation will help in the treatment of future patients with an understanding of how an implant affects breastfeeding and on the optimal timing of starting the implant to prevent unplanned pregnancies.

19.3 The direct benefits from the contraceptive implant include improved access to the device in either randomization arm: immediate access prior to hospital discharge or help from research staff scheduling clinic appointment for placement. Direct medical benefits from the implant include improved autonomy related to their reproductive health, ability to control when they want to become pregnant again given the high contraceptive effectiveness and ease of use of the implant, longer intervals between pregnancies which is associated with improved maternal and neonatal outcomes, and improvement in menstrual bleeding/reduction in anemia. The implant is a popular contraceptive choice for adolescents, who often prefer a long-acting method that does not require a pelvic examination. These benefits of the contraceptive implant are part of the reason that minors do not need parental consent to have the implant placed clinically.

## **20. Recruitment Methods**

20.1. (Also described under “procedures” in Section 12.) Patients may be recruited in the following locations/timeframes: 1) antenatal clinics, 2) visits to OB-Triage 2) on admission to L&D for delivery not in active labor or 4) during the first postpartum hours in the Ob-Gyn ward of the UNM Hospital and University of Utah Hospital.

- Patients may be asked for their contraceptive choice in any of these four venues, although ideally in antenatal clinics during prenatal care. When women decide on an implant as a postpartum contraceptive in any of these venues, the PCP (Ob-Gyn, Family Medicine physicians/residents and midwives) may discuss the patient’s interest in hearing about the study and may contact the research coordinator by a message in the EMR or by phone or in person to let her know that the patient is interested in hearing about the study.
- Additionally, the research coordinator will review antenatal clinic, OB Triage and inpatient (L&D and postpartum) lists to assess patients’ contraceptive plan through review of the EMR. The research coordinator may contact patients who have decided on a postpartum implant to assess her interest in participating in the study.
- If the patient expresses interest, the research coordinator will present the study and ask the patient for her interest in enrolling. If interested, the research coordinator and/or a study co-investigator will explain the study, screen the patient for eligibility and obtain informed written or electronically signed consent.
- Women will not be approached for study participation if they are in active labor. Women will be approached and enrolled, if interested, either prior to active labor (e.g., when admitted for induction of labor or scheduled cesarean delivery) or after delivery.
- We will not enroll patients who are under sedation. Most participants will be enrolled and undergo informed consent in the antenatal period; some will be

**PROTOCOL TITLE:** Effect of immediate versus standard postpartum insertion of the contraceptive implant on breastfeeding outcomes

enrolled when they are admitted to labor and delivery not in active labor; neither of these two groups would be under sedation. For those “up to 22 hours after delivery,” we will only enroll women who have not received sedation within a 4-hour period.

- Once the woman is enrolled in the study a line will be added to the Antenatal Supplemental Visit Form stipulating the patient’s participation in the study and the coordinator’s phone number: Ex: [name] study patient – page at admission ####-####\*\*. This Form is a section of the EMR that is updated at each visit by the clinic provider with important/current antenatal issues; it is standard that the contraceptive plan for each patient is recorded here.

**Identification of study patients on L&D**

- The PCP on L&D may identify study patients who self-identify as being in the study. They will also be alerted by the “Study Patient” in the antepartum record if the patient has been enrolled antepartum. They will notify the research coordinator who will carry a phone during working hours.
- A reproductive health on-call fellow/attending will be designated 24-7 to ensure randomization and implant insertion within 24 hours for those randomized to the immediate group. After hours (nights and weekends), the research cell will forward to the reproductive health on-call fellow or attending. In addition, the voice message for the research cell will direct callers to contact the reproductive health on-call fellow through Amion, the hospital online paging system. A calendar will specify which co-investigator is on call for study patients.
- The PCP on L&D will call the research coordinator/call physician by phone or by text message that a study patient arrived on L&D for her birth.

20.2. The research coordinator will review the list of admitted patients to L&D twice a day (8 AM and 4 PM) and once daily on Mother Baby Unit and Ob-Special care the (Ob-Gyn wards) to identify enrolled study patients. This modality has been used with other studies in the department of Ob-Gyn and has been successful.

20.3. Brochures and flyers will be used to recruit participants. See attached documents.

**21. Provisions to Protect the Privacy Interests of Subjects**

21.1. We will take measures to protect the security of all personal information, but we cannot guarantee confidentiality of all study data. To minimize the privacy risk, the research team will reassure the patient of the following:

Information contained in study records is used by study staff alone. The University of New Mexico and other recruitment sites’ Institutional Review Board (IRB) that oversee human subject research and/or other entities may be permitted to access records. Additionally, de-identified data will be shared for reporting to the DSMB, if needed, as well as for final data analysis and reporting. There may be times when we are required by law to share information. However, protected health information (PHI) will not be used in any published reports about this study.

**PROTOCOL TITLE:** Effect of immediate versus standard postpartum insertion of the contraceptive implant on breastfeeding outcomes

There will be a need for medical record access to assess patient demographics and clinical outcomes. Most study data will be stored in the HIPAA-secure de-identified online REDCap database. Any printed study data (such as signed consent forms) will be secured in a locked cabinet/file-box and only those directly involved in the study will have access to this including the investigators who will process it. Only de-identified data will be saved under a secure file on a computer requiring a log-in password. Data will be stored for five years, and then will be destroyed.

21.2. A description of this clinical trial will be available on <http://www.ClinicalTrials.gov>, as required by U.S. Law.

21.3. A study participant's privacy interests during recruitment and data collection will be protected through the following measures:

The study will be thoroughly explained to the potential participant using the HRPO-approved consent form. As part of the informed consent process, the recruiting co-investigator or research assistant will provide as much time as needed for the potential participant to consider study participation. If any privacy interests are expressed by the patient, they will be addressed immediately by the research team member and if necessary, the issue will also be considered by the principal investigator.

Participants will be recruited and consented in a private clinic setting. This will also include the recruitment and screening process as well as the data collection procedures.

## **22. Economic Burden to Subjects**

22.1. Participant's third party payer (i.e. insurance company) is responsible for all the costs related to the implant and clinical treatment. This would be the case regardless of study involvement.

New Mexico Medicaid reimburses for immediate postpartum implant placement (prior to hospital discharge) and will cover all costs related to the implant and clinical treatment. Private insurers do not cover the costs. We will be enrolling participants that are Medicaid, uninsured, underinsured and private insurers, until the supply of 33 implants run out. We do anticipate receiving additional no-cost implants; if this occurs, we will continue enrollment of private insured and un or under-insured women. Please see the table below.

Research Procedures	Number of Samples/Procedures	Responsible Party	
		Study	3rd Party Payer or Participant
Immediate implant insertion	75		
			
			

PROTOCOL TITLE: Effect of immediate versus standard postpartum insertion of the contraceptive implant on breastfeeding outcomes

_____	_____		
_____	_____		
_____	_____		
_____	_____		
_____	_____		
Standard of Care Procedures		Number of Samples/Procedures	Responsible Party
Implant insertion at 4-6 weeks		75	Study  3rd Party Payer or Participant 
_____	_____		
_____	_____		
_____	_____		
_____	_____		
_____	_____		
_____	_____		
_____	_____		
_____	_____		

